#### 1.0 Background/Rationale:

Recent developments in hepatitis C virus (HCV) therapeutics, notably the introduction of interferon-free directly acting antiviral (DAA) regimens, have revolutionised the treatment landscape providing the potential to scale up therapy across broad populations living with HCV, including those in low and middle income countries (LMIC). Although costly, increasing production of generic alternatives to pharma marketed supply, including generic versions of sofosbuvir and daclatasvir, mean that relatively cheap courses of DAA combinations can now be purchased by individuals and governments to facilitate access for affected communities.

The extremely high efficacy and low toxicity of these regimens have also revolutionised the potential approach to treatment monitoring. Rates of on-treatment virological suppression close to 100% mean that on-treatment virological monitoring is no longer required, simplifying HCV RNA testing requirements to two time-points, a pre-treatment and SVR12 HCV RNA qualification. Further, the incredibly low rate of adverse events (equivalent to placebo) and minimal treatment drop-out rates mean that toxicity or safety monitoring can also be reduced to a minimum. These changes have major implications for the delivery of therapy on a broad scale, especially in countries where resources are limited.

However, major challenges still remain, particularly around the simplification of diagnostic and testing methodology . Currently, the HCV testing algorithm involves the detection of HCV antibodies to confirm exposure followed by HCV RNA or core antigen testing to detect active infection. This two-step process to confirm active infection requires multiple visits and results in a loss of patients diagnosed with HCV infection. In addition to multiple visits, HCV RNA determination (qualitative or quantitative) requires the collection and preparation of plasma in a standardised laboratory, with resultant significant expense and complexity, providing a major barrier to testing in many situations. Point-of-care HCV testing using oral fluid and fingerstick capillary blood rapid diagnostic testing has been shown to increase testing and linkage to care 6-10 However, many currently available point-of-care tests only measure HCV antibodies, not HCV RNA. More recently the development of rapid point-of-care (POC) tests to enable HCV RNA detection in the clinic (e.g. Xpert® HCV Viral Load, Cepheid®) has shown potential for implementation. Currently, the only two CE-marked point-of-care HCV RNA assays (the Xpert® HCV Viral Load, Cepheid and the Genedrive® HCV ID Kit, Genedrive) both require venepuncture, which is challenging in settings without access to phlebotomists or among people with poor venous access, including people who inject drugs 13. Further

improvements to this technology have demonstrated HCV RNA can also be detected in fingerstick capillary blood (Grebely Lancet Gastro 2017, and Lamoury under review).

Methodology involving the collection and testing of dried blood spot (DBS) for HCV RNA and/or HCV core antigen has further potential for significantly upscaling testing by simplifying linkage from the clinic through to treatment and care. Although showing great promise these new technologies require validation against the current gold standard of plasma HCV RNA quantification, both in resource rich and resource limited settings.

Myanmar is one of the designated 91 LMIC able to purchase generic DAA therapy without challenging patent. Approximately 2,000 courses of generic sofosbuvir/daclatasvir have recently been obtained by the National Hepatitis Control Program to be allocated to HCV patients (HIV positive and negative) in an initial roll-out of therapy to 5 treatment sites including Specialist Hospital Mingaladon and Specialist Hospital Waibargi in Yangon in 2017. Following the initial roll-out, a further 4,000 courses are expected to become available in 2018-2019. Additionally, a collaborative project between USAIDS and Myanmar Liver Foundation is expected to supply 4,000 treatment courses of sofosbuvir/velpatasvir +/ribavirin commencing 2018 over 5 years, of which 20% will be allocated to people with HIV coinfection.

Specialist Hospital Mingaladon is one of the largest HIV treatment hospitals in Myanmar with an estimated 8,000 HIV positive patients, the majority of whom are maintained on ART (first line TDF/3TC/EFV, alternatives AZT/3TC/EFV and ABC/3TC/EFV plus second line (ritonavir boosted lopinavir (LPV/r) or atazanavir (ATV/r)). Median CD4 count at ART initiation is approximately 230 cells/mm³, with the majority of patients maintained on first line ART. Due to the lack of free treatment, HCV antibody testing was not carried out routinely until June 2016. Routine testing of newly recruited HIV patients and old cohorts were made after June 2016 when the National Hepatitis Control Program pledged to start free treatment. As of February 2018, more than 7000 patients were tested and 359 were HCV antibody positive (5%), of which about 50 were either dead or lost to follow up. The first round of HCV treatment started at Mingaladon Hospital in June 2017 and approximately 260 patients were treated to already warehoused patients with sofosbuvir and daclatasvir. For HCV RNA testing, plasma is collected at Mingaladon Hospital and the samples are sent on the same day to the National Health Laboratory to be tested using GeneXpert module 4.

National Hepatitis Control Program is trying to implement free HCV treatment centres in large cities throughout the country but HCV diagnosis done on plasma at central specialised laboratory is a limiting factor. Fingerstick testing and running on GeneXpert machine has the potential for point-of-care service, with result turn-around time of an hour, minimising patient

visits and dropouts. DBS is easier to collect and easier to be transported to the central laboratory with smaller sample volume and transportation restrictions.

Collection of DBS at the local site at time of patient review is highly feasible and will allow comparison of the performance of both cAg and HCV RNA in DBS against the local gold standard. The anticipated delivery from 2018 onwards of approximately 200 plus treatment courses of sofosbuvir/daclatasvir to HIV-HCV co-infected patients at Specialist Hospital Mingaladon, followed by additional sites and regimens including sofosbuvir/velpatasvir, provides an invaluable setting in which to evaluate a number of key concepts critical for widespread HCV diagnostic and treatment uptake in LMIC settings.

# 2.0 Hypotheses

- Simplified virological and safety monitoring during and following DAA therapy is an effective and safe management strategy in a resource limited setting
- Novel diagnostic methods for HCV detection including DBS collection and fingerstick capillary HCV RNA testing (GeneXpert, Cepheid) will perform in an equivalent manner to standard plasma HCV RNA methodology

## 3.0 Objectives

## 3.1 Primary objective

To evaluate the proportion of patients with undetectable HCV RNA at 12 weeks post-treatment (SVR12) following a course of DAA therapy delivered using a simplified schedule of safety and virological monitoring.

#### 3.2 Secondary objectives

- 1) To evaluate acceptability and feasibility of DBS collection in Myanmar.
- 2) To evaluate concordance pre and post therapy between HCV RNA (fingerstick) and standard plasma HCV RNA detections.
- 3) To evaluate concordance pre and post therapy between HCV core antigen (DBS) and standard plasma HCV RNA detections.
- 4) To evaluate concordance pre and post therapy between HCV RNA (DBS) and standard plasma HCV RNA detections.
- 5) To evaluate patients' knowledge on HCV by using set-up questionnaire.
- 6) To understand HCV virus patterns in Myanmar through phylogenetic sequencing.
- 7) To enhance and develop laboratory and research capacity at Specialist Hospital Mingaladon (SHM), Specialist Hospital Waibargi (SHW) and Insein General Hospital (IGH).

# 4.0 Methodology

A total of 200 HIV HCV co-infected patients who visit out-patient department of SHM/SHW/IGH from 2018 onwards will be enrolled by simple random sampling.

In addition to the procedures for their usual medical care, each participant will complete a questionnaire and require blood sample collection (extra 5 ml) at baseline (fingerstick and venepuncture) and at SVR12 (fingerstick alone).

Proportion of participants achieving SVR will be calculated. Concordance between standard of care method and new DBS method will be evaluated. Analysis will be performed using STATA (version 14.0; Stata Corporation, College Station, TX).

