**Table 1. Scheduled assessments** 

Assessment / Procedure	Screening/baseline	Follow-up
Study weeks	-6 to 0	24 (SVR12)
Informed consent, medical history, risk	Х	
behaviour		
Liver function tests/ Full blood count/	Х	Х
eGFR		
HIV RNA/ CD4 count	x	Х
HCV-RNA testing (NHL) (Xpert®)	Х	Х
Finger stick capillary blood (Xpert®) a	Х	Х
Plasma store for HCV RNA b (Abbott)	Х	Х
Dried blood spot c (Abbott/Architect)	Х	Х

NHL = National Reference Laboratory

<sup>a Capillary blood collected by fingerstick and transferred to UM2 laboratory for HCV RNA testing using GeneXpert machine

<sup>b A single plasma store will be collected and stored at -70°C for HCV RNA testing, plus future immunovirological research as allowed including HBV validation

<sup>c Fingerstick capillary blood air dried on filter paper and temporarily stored at -20°C at Mingaladon, then sent to Kirby Institute for HCV and HBV testing and future immunovirological research

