# 6.3 Virological testing

The following virological methodology will be employed:

- 1. Standard Plasma HCV RNA testing
  - a. Myanmar

A plasma sample will be taken pre-treatment initiation to confirm active HCV viremia before commencement of therapy. This sample will be sent to the National Health Laboratory in Yangon for testing as per the Myanmar HCV treatment guidelines. Current testing is with the GeneXpert technology (module 4).

b. International

A single HCV RNA plasma store will be collected and stored at -70°C and batch shipped to VHCRP at Kirby Institute at the close of the study. The sample will be analysed for HCV RNA by Abbott M2000 RT machine, as an international standard to cross-validate DBS and local lab result.

- 2. Finger stick capillary blood sample (research).
  - A sample of whole blood will be collected via finger-stick for a HCV point of care test. This sample will be used to test HCV viral load via the Xpert® HCV Assay performed on the GeneXpert instrument system at the research laboratory. This test uses reverse transcriptase polymerase chain reaction (RT-PCR) and provides a measure of HCV RNA levels within 60 minutes.
- 3. Dried blood spot collection (DBS) for HCV core antigen and HCV RNA testing (research).

A finger-stick whole-blood sample will be collected for the dried blood spot sample collection using a (MiniCollect Safety Lancet; Greiner Bio-One, Monroe, Frickenhausen, German). Five spots (depending on available blood) of capillary whole-blood collected by finger-stick will be collected on dried blood spot cards, airdried, transferred to -20°C and batch shipped to VHCRP at Kirby Institute at the close of the study. In VHCRP lab DBS will be analysed for the presence of HCV, including HCV core antigen and HCV RNA.

Participants will not receive the results of any of the research samples as these are not accredited assays.

[figure not shown]

Fig 2. Diagnostic methods to be used

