## 7.3 Sample size

The sensitivity and specificity of the Abbott RealTime HCV assay on dried blood spot samples will be compared with the Abbott RealTime HCV assay on plasma samples collected via venepuncture. Assuming an SVR of 95%, (n=100, one sample at BL and SVR12, total n=200), a sensitivity and specificity of 95%, 200 samples would provide a 95% confidence interval of 89-98% for the estimates of sensitivity and specificity. Assuming an SVR of 95%, (n=150, one sample at BL and SVR12, total n=300), a sensitivity and specificity of 95%, 300 samples would provide a 95% confidence interval of 90-98% for the estimates of sensitivity and specificity. Assuming an SVR of 95%, (n=200, one sample at BL and SVR12, total n=400), a sensitivity and specificity of 95%, 400 samples would provide a 95% confidence interval of 91-98% for the estimates of sensitivity and specificity.

The sample size for the study is n=200 patients (n=400 samples) to provide a sensitivity/specificity of 95% with a 95% CI of 91-98%.

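### The protocol contradicts itself on whether Abbott reference plasma is taken at SVR12; without it, the specificity precision planned in Section 7.3 is lost

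*Protocol*

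**What the plan says.** Two parts of the protocol point to research plasma at baseline only.

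- **Section 4.0.** Participants will "require blood sample collection (extra 5 ml) at baseline (fingerstick and venepuncture) and at SVR12 (fingerstick alone"). The sentence opens "In addition to the procedures for their usual medical care, each participant will complete a questionnaire", so the restriction covers research blood and not usual-care blood.
- **Section 6.2.** The extra 5 ml of venous blood is described at the entry visit. The paragraph on the visit 12 weeks after treatment describes an interview and a clinical assessment, with no research draw.

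Two parts require it at both visits.

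- **Table 1.** The row "Plasma store for HCV RNA" (Abbott) is marked at screening/baseline and at SVR12.
- **Section 7.3.** The comparison being sized is Abbott RealTime on DBS against Abbott RealTime on venepuncture plasma, with "n=200, one sample at BL and SVR12, total n=400". It is said to give 91–98% around a sensitivity and specificity of 95%.

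Two statements leave the matter open. Footnote b to Table 1 says "A single plasma store will be collected and stored at -70°C for HCV RNA testing", and Section 6.3 item 1b says "A single HCV RNA plasma store will be collected and stored at -70°C". Neither says whether this means one store per visit or one per patient.

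Section 6.3 item 1a, "A plasma sample will be taken pre-treatment initiation to confirm active HCV viremia before commencement of therapy", concerns the National Health Laboratory Xpert test and does not bear on the Abbott plasma.

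**The concern.** A site that works from Section 4.0 would take no Abbott plasma at SVR12, while the sample-size statement depends on it. Nearly all patients are expected to be RNA-positive before treatment and RNA-negative after it, so the post-treatment samples supply the negatives from which specificity is estimated. Specificity of DBS RNA and of DBS core antigen are secondary endpoints (Section 7.2), and secondary objectives 3 and 4 ask for concordance both before and after therapy.

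Plasma that is not drawn cannot be recovered. Samples are shipped in a batch at study close, so the gap might not be noticed until then.

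**Working it through.** **Inputs (Section 7.3).** 200 patients; one DBS/plasma pair at baseline and one at SVR12; SVR 95%; sensitivity and specificity 95%; stated 95% CI 91–98%. The model treats every baseline sample as RNA-positive and assumes that every patient contributes at both visits.

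**Formula.** Exact (Clopper-Pearson) 95% CI for x successes in n: lower = B(0.025; x, n−x+1), upper = B(0.975; x+1, n−x). B is the beta quantile and x = 0.95n, left unrounded where it is not whole.

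**Step 1: reproduce the plan.** With the number of patients as denominator, all three stated intervals are recovered.

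| Patients (n) | Exact 95% CI | Stated in 7.3 |
|---|---|---|
| 100 | 88.7–98.4 | 89–98 |
| 150 | 90.2–97.9 | 90–98 |
| 200 | 91.0–97.6 | 91–98 |

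A denominator of 400 gives 92.4–96.9, which does not match. At n=200, Wilson (91.0–97.3) and Wald (92.0–98.0) do not match either. The stated precision therefore needs about 200 samples in each class.

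**Step 2: where the classes come from.**
- Reference-positive: 200 at baseline + 5% × 200 = 10 at SVR12, total 210.
- Reference-negative: 95% × 200 = 190, all from SVR12.

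**Step 3: remove the SVR12 Abbott plasma.** Pairs fall from 400 to 200, a loss of 50%. Positives fall from 210 to 200 and negatives from 190 to 0.

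**Step 4: allow for RNA-negative participants at baseline.** Eligibility rests on HCV antibody (Section 4.2), and entry is on the day blood is drawn, before the RNA result is known (Section 6.2), so some may be enrolled. Sections 4.1 and 5.0, however, describe patients who are to start DAA therapy. The protocol gives no proportion, so the last four rows below are assumptions.

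| Scenario | Abbott pairs | Positives: n, CI for 95% | Negatives: n, CI for 95% |
|---|---|---|---|
| Plasma at both visits (Table 1, 7.3) | 400 | 210: 91.1–97.5 | 190: 90.9–97.6 |
| Baseline only, all RNA-positive | 200 | 200: 91.0–97.6 | 0: not estimable |
| Baseline only, 10% negative | 200 | 180: 90.7–97.7 | 20: 75.1–99.9 |
| Baseline only, 20% negative | 200 | 160: 90.4–97.8 | 40: 83.1–99.4 |
| Baseline only, 30% negative | 200 | 140: 90.0–98.0 | 60: 86.1–99.0 |
| Baseline only, 40% negative | 200 | 120: 89.4–98.1 | 80: 87.7–98.6 |

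The sensitivity interval hardly moves in any row. The specificity interval is absent or wider than planned in every baseline-only row.

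**The case against.** The strongest reply is that plasma RNA is still measured at SVR12. Section 4.0 limits only blood taken beyond usual care. Table 1 marks the National Health Laboratory Xpert test at both visits, and Section 6.1 makes an RNA test 12 weeks after treatment part of usual care. The objectives and endpoints refer to standard plasma HCV RNA without naming Abbott, and Section 1.0 speaks of "comparison of the performance of both cAg and HCV RNA in DBS against the local gold standard". This stands. A reader might infer that objectives 3 and 4 fail after therapy, or that all specificity is lost; the documents do not support that. If the SVR12 specimen is plasma, as at baseline, specificity of fingerstick Xpert and of DBS against the local test can be estimated. The protocol does not spell out that specimen type. Nor need falling back on Xpert mix two reference assays: it is scheduled at both visits and could serve as one consistent reference. It is simply not the reference on which Section 7.3 is built.

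A second reply is that Section 6.2 closes by referring to the schedule of assessments, so sites may follow Table 1, where *single* reads naturally as one store per visit. That lowers the chance of harm but leaves the explicit wording of Section 4.0 in conflict.

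Two further inferences should be resisted. Section 1.0 reports about 260 treated among 359 antibody-positive patients, some 50 of whom were dead or lost. The untreated remainder is not a count of RNA-negatives, because patients may be untreated for other reasons. And although only about 10 positives are expected after therapy, Section 7.3 pools the visits and does not claim 91–98% for post-therapy sensitivity.

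**Conclusion.** The contradiction is real, and it affects the one comparison that Section 7.3 sizes. Following Section 4.0 costs 200 of 400 Abbott pairs and all of the roughly 190 modelled reference-negatives. The 91–98% interval for specificity against Abbott plasma then has no basis: specificity is either inestimable or imprecise, depending on an unstated number of RNA-negative enrolees. The corresponding sensitivity interval is essentially unchanged.

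The size of the loss rests on Section 7.3's own assumptions of 95% SVR and complete pairs at both visits. It arises only where sites act on Section 4.0 in preference to Table 1. The primary SVR12 endpoint is untouched, since it can rest on the usual-care RNA test. The point should still be corrected before sampling, because the remedy is mostly wording and the loss is permanent.

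**What to change.** 1. In Sections 4.0 and 6.2, state that research venous plasma for Abbott RealTime is collected at baseline and at SVR12, as Table 1 and Section 7.3 already require.
2. In Section 6.3 item 1b and footnote b, replace *single* with one store per visit. Leave item 1a as the National Health Laboratory Xpert test.
3. Name Abbott plasma as the reference for DBS RNA and DBS core antigen at both visits.
4. Align the stated research blood volumes. Sections 4.0 and 6.2 give an extra 5 ml and Section 10.2 an additional 4 ml.

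If research plasma will not be taken at SVR12, restate Section 7.3 as 200 Abbott pairs and withdraw the 91–98% specificity figure for that reference. Then name the National Health Laboratory Xpert result as the reference at both visits, and confirm that its SVR12 specimen is plasma.

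The first course costs up to 5 ml more blood per participant at a visit where Table 1 already schedules blood tests, plus an update to the ethics and consent wording. The alternative takes no extra blood but gives up the Abbott comparison after therapy.

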# 4.1 Study Population

All HIV-HCV coinfected patients planned to commence DAA therapy at Specialist Hospital Mingaladon and Waibargi +/- other treatment sites during the time period of the study

#### 4.2 Inclusion criteria

Subjects must meet all of the following inclusion criteria to be eligible to participate in this study.

- 1) Have voluntarily signed the informed consent form.
- 2) 18 years of age or older.
- 3) HCV antibody
- 4) HIV antibody positive

#### 4.3 Exclusion criteria

Subjects who meet any of the exclusion criteria are not to be enrolled in this study.

- 1) Clinically significant illness (other than HCV) or any other major medical disorder that may interfere with the participant treatment, assessment or compliance with the protocol
- 2) Creatinine clearance (CLcr) < 30 mL/min at screening
- 3) Pregnant or nursing female.
- 4) Use of prohibited concomitant medications.
- 5) Inability or unwillingness to provide informed consent or abide by the requirements of the study.

# 4.4 Study sites

- Specialist Hospital Mingaladon
- Specialist Hospital Waibargi
- +/- Insein General Hospital (if HCV treatment program is being rolled out to include that hospital)

## 4.5 Study duration

Two years, starting from the launch of second round of HCV treatment, probably June 2018. The majority of warehoused HCV-HIV co-infected patients were already treated in the first round. Assuming 5-8 new patients per month at each Specialist Hospital, two years will elapse to reach the sample size of 200.

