# **6.0** Study Procedures

#### 6.1 Standard of care

Serological screening for viral hepatitis infection is now routinely done at both Specialist Hospitals Mingaladon and Waibargi. Those who tested positive for anti-HCV antibody by WHO pre-qualified test kit (SD Bioline) and who meet the treatment eligible criteria by "Simplified Treatment Guideline for HCV Infection, Myanmar" (i.e. normal renal function, not pregnant, older than 18 years and not taking anti-TB drugs), will be given an appointment (first visit of HCV care). On that day, 10 ml of blood (6 ml for RNA, 1 ml for CBC and 3 ml for biochemistry) will be drawn for testing HCV RNA and other baseline tests. Three millilitres of plasma will be put in ice-box and sent to National Health Laboratory on the same day to test HCV RNA by GeneXpert 4 module machine. Baseline investigations are complete blood count (CBC), serum creatinine, ALT and ultrasound of the abdomen.

All patients will be given one week's appointment to enquire results (second visit of HCV care). Those with detectable HCV viral load (> 10 IU/ml) are offered DAA (Direct Acting Antivirals: sofosbuvir + dose adjusted daclatasvir). APRI score (ALT platelet ration index) is calculated. Significant fibrosis is defined as clinical cirrhosis with signs of chronic liver insufficiency and ascites, or fibrosis/cirrhosis on ultrasonography, or APRI score >2. The duration of treatment is 12 weeks for non-cirrhosis and 24 weeks for cirrhosis. Drugs are to be picked up monthly. Cure is determined by undetectable HCV RNA 12 weeks after completion of treatment.

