# 6.6.2 Dried Blood Sample

Dried blood spot specimens will be collected by applying a few drops of blood, drawn by lancet from the finger, onto an absorbent filter paper. The blood is allowed to thoroughly saturate the paper and is air dried for a few hours. Specimens will be transferred into plastic bags with desiccant added to reduce humidity. These samples will be stored at -20°C at CRL and batch-shipped to VHCRP at Kirby Institute at the close of the study. In VHCRP lab DBS will be analysed for the presence of HCV, including HCV core antigen and HCV RNA. The samples will not be stored at VHCRP. After analysis, the samples will be discarded.

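### Section 4.5 uses the same two years as accrual time and as total study duration: the stated rate reaches 200 in 12.5-20 months, and if accrual does take two years no time remains for SVR12

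*Protocol*

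**What the plan says.** Protocol section 4.5 gives the study duration as "Two years, starting from the launch of second round of HCV treatment, probably June 2018". The accrual assumption and the conclusion drawn from it follow in the same section: "Assuming 5-8 new patients per month at each Specialist Hospital, two years will elapse to reach the sample size of 200".

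The other elements of the timeline are spread over the protocol:

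- Section 4.4 names two Specialist Hospitals, Mingaladon and Waibargi. Insein General Hospital is a possible third site if the treatment programme extends to it.
- Section 5.0 lets patients enter throughout the study period.
- Section 6.1: "The duration of treatment is 12 weeks for non-cirrhosis and 24 weeks for cirrhosis".
- Section 7.1 measures the primary endpoint at least 12 weeks after therapy ends. Table 1 in section 6.2 places the SVR12 visit at study week 24, after a screening window of up to 6 weeks.
- Section 7.3 counts one baseline and one SVR12 sample per patient: "The sample size for the study is n=200 patients (n=400 samples").
- Section 6.6.2 has the dried blood spots "batch-shipped to VHCRP at Kirby Institute at the close of the study". Section 6.3 gives the same timing for the stored plasma. No date or event defines the close.

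No follow-up period after the last enrolment is stated.

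**The concern.** Two things do not fit. First, two hospitals at the stated rate should reach 200 well before two years, so the rate, the target and the duration disagree unless something unstated lies between new patients and enrolled participants. Second, the two years are spent entirely on reaching 200, although the last patient enrolled still needs a full course of treatment plus 12 weeks before the primary endpoint can be measured.

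If the study closes on the stated date, the patients enrolled last have no SVR12 result or SVR12 research samples within the study period. The same samples supply most of the HCV-negative specimens for the specificity estimates in section 7.2: patients are generally viraemic at baseline, and section 7.3 assumes 95% are cured at SVR12. Because shipment is tied to an undefined close, late SVR12 samples could also miss the batch.

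**Working it through.** **Inputs.** Target 200 patients (4.5, 7.3). Rate 5-8 a month per Specialist Hospital (4.5). Two Specialist Hospitals (4.4). Treatment 12 or 24 weeks (6.1), plus at least 12 weeks to the endpoint (7.1), so 24 or 36 weeks from the start of treatment. Screening window up to 6 weeks (Table 1), so at most 30 or 42 weeks from enrolment. Weeks per month = 365.25 / 12 / 7 = 4.348.

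**Step 1: try to reproduce the stated 24 months.** Months to accrue = 200 / (sites x rate per site).

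| Sites | 5 a month | 6.5 a month | 8 a month |
|---|---|---|---|
| 1 | 40.0 | 30.8 | 25.0 |
| 2 | 20.0 | 15.4 | 12.5 |
| 3 | 13.3 | 10.3 | 8.3 |

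With two hospitals the range is 12.5-20 months. The optional third site moves it further from 24. One site comes near 24 only at the top rate, and section 4.5 gives the rate for each hospital.

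In reverse, 24 x 10 = 240 and 24 x 16 = 384 patients in two years. Reaching exactly 200 in 24 months needs 200 / 24 / 2 = 4.2 a month per hospital, below the stated range.

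**Step 2: the enrolment fraction that would reconcile the figures.** 200 / 384 = 52% and 200 / 240 = 83%.

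**Step 3: late entrants if accrual does take 24 months.** Uniform accrual is assumed, at 200 / 24 = 8.33 a month, with all 200 treated. Number reaching SVR12 after month 24 = 8.33 x (weeks / 4.348).

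| Time to SVR12 | Months | Patients | Share of 200 |
|---|---|---|---|
| 24 weeks (12-week course) | 5.5 | 46 | 23% |
| 30 weeks (with full screening window) | 6.9 | about 58 (57.5) | 29% |
| 36 weeks (24-week course) | 8.3 | 69 | 35% |
| 42 weeks (with full screening window) | 9.7 | about 81 (80.5) | 40% |

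The last two rows would require every late entrant to have a 24-week course. They are an upper bound, because the protocol does not give the share with cirrhosis.

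**Step 4: last SVR12 at the stated rates, if every new patient enrols.** Two hospitals, 12-week course, screening window not counted:

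- 5 a month: 20.0 + 5.5 = 25.5 months
- 6.5 a month: 15.4 + 5.5 = 20.9 months
- 8 a month: 12.5 + 5.5 = 18.0 months

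Having all 200 at SVR12 by month 24 on a 12-week course needs at least 200 / (24 - 5.52) / 2 = 5.4 a month per hospital.

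**Step 5: total duration that covers the last SVR12 visit, with the full screening window.** At the stated rates, from 12.5 + 6.9 = 19.4 to 20 + 9.7 = 29.7 months. With 24 months of accrual, from 24 + 6.9 = 30.9 to 24 + 9.7 = 33.7 months.

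**The case against.** Four points can be made for the protocol, and each has some force.

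*The rate counts new patients, not participants.* Exclusions (4.3), programme eligibility (6.1) and voluntary consent (10.1) all lie between the two, and enrolment of 52-83% would be an ordinary allowance. This stands as a possible explanation. The rate and the two years are therefore unreconciled rather than proved incompatible, but the fraction that would reconcile them is not given.

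*Nothing stops follow-up at month 24.* Section 6.2 schedules a post-treatment assessment for all patients, and section 6.1 makes the test of cure part of programme care. A reader might infer that up to 40% of patients will have no primary outcome. The documents do not support that: late entrants may well be tested, only after the stated period. The 40% also needs a 24-week course for everyone.

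*The timeline works at the higher rates.* At 6.5-8 a month per hospital, all 200 on a 12-week course reach SVR12 within two years. It is therefore not true that the plan leaves no time for SVR12 at every rate. The shortfall follows from the statement that accrual takes two years, and from the low end of the stated rate.

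*The counts may be somewhat high.* The 6-week window is a maximum, and section 6.1 has patients return for results after one week. Entry is by antibody and occurs before the RNA result (4.2, 6.2), so any non-viraemic entrants would have no SVR12 due.

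**Conclusion.** The stated duration is wrong as written. Two years cannot be both the time to enrol the last of 200 patients and the length of a study whose primary endpoint comes at least 24 weeks after treatment starts. Nor do two years follow from the stated rate without an unstated enrolment fraction.

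If section 4.5 is taken at its word, about 46 of 200 patients (23%) reach SVR12 after the stated period, or about 58 (29%) with the full screening window. This assumes uniform accrual over 24 months, all 200 treated, and 12-week courses. The 69-81 figure is an upper bound only.

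What is at risk is the availability of late entrants' results and research samples within the study period. Sensitivity would be little affected, because baseline samples are already in hand; the loss falls mainly on specificity. A reader might also infer that the SVR12 confidence interval would fall short of 91-98%. Section 7.3 gives that interval only for sensitivity and specificity, and the protocol states none for SVR12, so that comparison cannot be made.

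This is a timeline error that changes no endpoint or analysis. It is worth correcting because it could cause avoidable missing outcomes, all among the last patients enrolled.

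**What to change.** In section 4.5:

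1. State the accrual time and the total study duration separately.
2. Either give the fraction of new patients expected to enrol that makes accrual 24 months (52-83% at the stated rates), or correct the accrual time to 12.5-20 months.
3. Extend the total duration to the last enrolled patient's SVR12 visit: about 19-30 months at the stated rates, or about 31-34 months if accrual takes 24.

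In sections 6.2, 6.3 and 6.6.2, define the study close that triggers batch shipment as falling after the last SVR12 sample has been collected.

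The cost is protocol wording and possibly a later end date. No extra patients are needed.
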